#### *Surfactant dose*

The licensed dose of surfactant for preterm infants with RDS is 100 to 200mg/kg. A dose of 200mg/kg reduces FiO2 requirements and the need for redosing as well as indicating possibility of reduced mortality and oxygen requirement at 36 weeks post menstrual age. A pharmacokinetic study has also demonstrated that a dose of 200mg/kg results in a higher half-life of surfactant compared to the 100mg/kg.

*Administration techniques*

The drive towards minimally invasive treatments for premature infants as well as the difficulties associated with intubation for surfactant delivery has led to innovations in surfactant administration. Minimally invasive surfactant administration (MIST) or less invasive surfactant administration (LISA) are techniques that use a thin catheter (Angiocath or nasogastric tube) to deliver surfactant whilst the infant is spontaneously breathing and this method is gaining popularity across Europe. A recent meta-analysis found that the use of LISA/MIST has reduced the composite outcome of death or bronchopulmonary dysplasia (BDP) at 36 weeks, need for mechanical ventilation within 72 hours of birth, or need for mechanical ventilation anytime during the neonatal intensive care stay.

Use of the LISA/MIST techniques of surfactant administration also supports the drive towards non-invasive methods of ventilatory support, as no intubation is required to instil the surfactant, in contrast to the intubate-surfactant-extubate (INSURE) method.

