### a. Comparative fields

In order to investigate whether surfactant dose affects neonatal outcomes, the following data will be obtained from the NNRDs:

	NNRD field	Purpose of using this field for this study
1	Demographics > Birth weight	Using this field alongside the volume of surfactant used, the dose of surfactant will be calculated.
2	Demographics > Sex of the baby (phenotypic)	Characterisation of cohort
3	Demographics > Gestation weeks and day	Inclusion/exclusion criteria
4	Antenatal > Were steroids given during pregnancy?	Characterisation of cohort
5	Antenatal > Number of antenatal steroid courses given	Characterisation of cohort
6	Labour & delivery > Methods of resuscitation	Characterisation of cohort
7	Labour & delivery > Drugs used during resuscitation	Characterisation of cohort
8	Labour & delivery > Was surfactant given during resuscitation?	Characterisation of cohort
9	Respiratory > Respiration: Surfactant given today	Inclusion/exclusion criteria
10	Discharge details > Discharge time and date (anonymised)	Duration of hospitalisation, age at discharge
11	Discharge details > Date of death and time - anonymised	Calculation of mortality
12	Discharge details > cause of death	Determination of outcomes
13	Discharge details > Discharge oxygen	To investigate whether the dose of surfactants can affect whether infants are discharged on oxygen.
14	Respiratory > Respiratory support device and support mode (daily)	To investigate whether using there is a correlation between surfactant dose and respiratory device
16	Discharge details > Clinical diagnoses at discharge	To correlate the dose of surfactant, and/or method of surfactant administration is related to clinical diagnoses at discharge
17	Retinopathy of prematurity > ROP stage*	To determine whether the dose of surfactant is related to the severity of retinopathy of prematurity
18	Cranial ultrasound scan > IVH**	To determine whether the dose of surfactant is related to the severity of periventricular haemorrhage

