## 6. Data Analysis

The primary objective of the study is to compare the two dosing groups (100-130 mg/kg and 170-200 mg/kg) in terms of the proportions of infants who require mechanical ventilation within four days of birth. This comparison will be undertaken primarily through propensity score matching with the key sensitivity analysis comparing the unmatched dosing groups.

The propensity score model will be a logistic regression model with binary 'outcome' corresponding to dosing group and with the following baseline factors included in the model; birth weight, gestational age, sex, antenatal steroids, inborn, age at first dose, and baseline FiO2. This analysis will be based on the modified Intention-to-Treat population (mITT) defined as all patients who satisfy the inclusion/exclusion criteria, who provide complete data on each of the baseline factors considered for inclusion in the propensity model and who are evaluable for the primary endpoint.

Following 1 to 1 matching between the dosing groups 100-130 mg/kg and 170-200 mg/kg using a caliper of 0.025, an analysis of the matched cohorts will be based on a logistic regression model with the primary endpoint, requiring mechanical ventilation within 4 days of birth, as the response and dosing group plus each of the covariates listed used in the propensity score model included as terms in this analysis model. The key sensitivity analysis will compare the dosing groups in the full mITT population using the same modelling structure.

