## The effect of surfactant dose on outcomes in preterm infants with RDS

NNUEpisodes	Labour & delivery	Drugs used during resuscitation	DrugsForResuscitation	NEONATAL RESUSCITATION DRUG (SNOMED CT DM+D)	n18	dm+d code for any drug	If medication was administered at resuscitation please select relevant medications.	Used to monitor neonatal outcomes
NNUEpisodes	Labour & delivery	Was surfactant given during resuscitation?	SurfactantGivenResuscitation	SURFACTANT GIVEN INDICATOR (DURING RESUSCITATION)	an1	N No Y Yes 9 Unknown	Surfactant given during resuscitation	Used to monitor neonatal outcomes
NNUEpisodes	Discharge details	Discharge date and time	DischDateTime	CRITICAL CARE DISCHARGE DATE AND TIME	an19	DateTime coding (e.g. 1997-07-16T19:20:30) Date (an10 CCYY-MM-DD) Time (an8 HH:MM:SS)	The date and time, Coordinated Universal Time (UTC), on which an inpatient completes this episode of care, either because of death, transfer to another ward or hospital, or because of discharge home.	Used to measure length of stay and to calculate the anonymised version of this field
NNUEpisodes	Discharge details	Date of death and time	DateofDeath	PERSON DEATH DATE AND TIME (DURING NEONATAL CRITICAL CARE PERIOD)	an19	DateTime coding (e.g. 1997-07-16T19:20:30) Date (an10 CCYY-MM-DD) Time (an8 HH:MM:SS)	The date and time, Coordinated Universal Time (UTC), on which an inpatient had died in this episode of care as stated on the death certificate. If the discharge destination indicates the infant died this item is required	Used in survival analyses and calculate anonymised dates

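### No primary-endpoint analysis in section 6 adjusts for calendar period, so a joint drift in dosing and ventilation practice would be counted partly as a dose effect

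*Protocol*

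**What the plan says.** Section 6 of the protocol fixes the adjustment at three places.

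- **Propensity model:** a logistic model for dosing group on "birth weight, gestational age, sex, antenatal steroids, inborn, age at first dose" and baseline FiO2. Infants are then paired by "1 to 1 matching between the dosing groups 100-130 mg/kg and 170-200 mg/kg using a caliper of 0.025".
- **Outcome model in the matched infants:** "dosing group plus each of the covariates listed used in the propensity score model included as terms in this analysis model".
- **Key sensitivity analysis:** "The key sensitivity analysis will compare the dosing groups in the full mITT population using the same modelling structure".

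The requested fields in section 3a include two dates, both marked as anonymised: "Discharge details > Discharge time and date (anonymised" and "Discharge details > Date of death and time - anonymised". Neither section 3a nor Appendix A lists a date, quarter or year of birth. Appendix A does list the discharge field as a full date and time, with the purpose "Used to measure length of stay and to calculate the anonymised version of this field".

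On changing practice, section 2a (Administration techniques) says of thin-catheter administration that "this method is gaining popularity across Europe", and cites a meta-analysis in which it reduced the need for mechanical ventilation within 72 hours. The protocol reports no trend in the dose given. Section 3 ends recruitment at 1300 infants and gives no duration.

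**The concern.** Clinicians choose the dose, often by whole vial (section 2b), so the comparison depends on the adjustment set. As specified, an infant born at the start of recruitment can be matched to one born at the end as if the two were exchangeable.

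Suppose the share of infants given the higher first dose rises during recruitment while ventilation becomes less common for other reasons. The higher-dose group then contains more late-born infants and is ventilated less often, whatever the dose does. If the two trends run in opposite senses, the bias has the opposite sign and could hide a real effect.

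The key sensitivity analysis changes the population from matched to unmatched but keeps the covariates. It shares the omission, so agreement between the two analyses would say nothing about drift. Section 5 has the original data destroyed after the final analysis, so a later repair may not be possible.

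**Working it through.** **The plan's own figures.** The protocol gives no figure for drift, so there is none to reproduce. The nearest is the total of 1300, which is needed here only for the number of matched pairs. The sample-size table does not follow from the usual formula: the unpooled calculation for 60% vs 45% at 80% power needs 171 per group, and 171 / 0.75 / 0.35 = 651.4, so 652, against 1303 stated. That is a separate matter and does not affect the check below.

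**Inputs from section 4a**
- Total 1300; 25% of the smaller dosing group unmatched; splits from 45%/45% to 35%/55%.
- Matched pairs: 1300 × 0.35 × 0.75 = 341 and 1300 × 0.45 × 0.75 = 439.
- Design effect: 60% − 45% = 15 points.

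**Assumptions (not in the protocol)**
- Two equal recruitment halves and no true dose effect.
- Among infants in the two dosing groups, the higher-dose share moves from q1 to q2. The ventilation rate moves from v1 to v2.
- The seven listed factors absorb none of the drift.

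**Formulas**
- Higher-dose rate = (q1·v1 + q2·v2) / (q1 + q2)
- Lower-dose rate = ((1 − q1)·v1 + (1 − q2)·v2) / (2 − q1 − q2)
- Spurious difference b = lower − higher = (v1 − v2)(q2 − q1) / [(q1 + q2)(2 − q1 − q2)]

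If the halves average to equal dosing groups, the denominator is 1 and b is the product of the two shifts. If either shift is zero, b is zero.

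**Middle case, q 40% to 60%, v 60% to 45%**
- Higher: 0.4 × 0.60 + 0.6 × 0.45 = 0.510
- Lower: 0.6 × 0.60 + 0.4 × 0.45 = 0.540
- b = 3.0 points, one fifth of 15.

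**False-positive rate.** Normal approximation for two proportions, with the variance taken at 52.5% throughout: SE = √(2 × 0.525 × 0.475 / n), which is 3.82 points at n = 341 and 3.37 at n = 439. The rejection probability is 1 − Φ(1.96 − b/SE) + Φ(−1.96 − b/SE). For b = 3.0 and n = 341, b/SE = 0.784 and the result is 0.120 + 0.003 = 0.123.

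| Higher-dose share | Ventilation rate | Spurious difference | Rejection, 341 pairs | Rejection, 439 pairs |
|---|---|---|---|---|
| 45% to 60% | 60% to 50% | 1.5 points | 6.8% | 7.3% |
| 40% to 60% | 60% to 45% | 3.0 points | 12.3% | 14.5% |
| 35% to 65% | 60% to 45% | 4.5 points | 21.8% | 26.6% |
| any | no change | 0 | 5% | 5% |
| no change | any | 0 | 5% | 5% |

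**Check on the split.** The 341 pairs come from a 35%/55% split, whereas the drift cases have equal or nearly equal groups. With an average higher-dose share of 35/90 or 55/90, the denominator is 4 × (35/90) × (55/90) = 0.951. The 3.0 points become 3.0 / 0.951 = 3.2, so the mismatch is minor.

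**The case against.** **The data may well allow adjustment.** A reader might infer from the two anonymised dates that calendar time has been stripped from the extract and cannot be adjusted for. The documents do not support that. Only the discharge and death dates are so marked. Section 5 excludes patient and Trust identifiers and does not mention period. Appendix A lists full date-time fields, and section 3 says the database is built from quarterly extracts. Eligibility itself depends on birth after the initiation date. Absence from the field list is weak evidence, because the list also lacks inborn status and time of birth, which the model's own covariates need. This objection stands in full. What remains is that no birth period is requested and none is said to be kept.

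**Bias is not established.** A reader might also infer that drift will be read as a dose effect. That needs dosing and ventilation to move together, beyond what the listed factors capture. The documented trend concerns administration method, no trend in dose is shown, and recruitment length is unknown. This stands too: the bias is conditional and every drift size above is assumed. The ventilation fall in the middle and stronger cases is as large as the whole design effect.

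**Period is only a proxy.** Administration method is recorded for each infant, and calendar period would capture only its time trend. That is true, but method is not in the covariate list either, and period also covers other secular changes in care.

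**The analysis plan could add it.** Section 6 refers to a key sensitivity analysis without excluding others, and its population definition speaks of factors considered for the propensity model. An added analysis is therefore possible. Even so, section 6 names the factors one by one and carries them into all three analyses, so a plan that follows it would leave period out.

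**Conclusion.** The concern holds as a conditional one. Calendar period is missing from the propensity model, the outcome model and the key sensitivity analysis of a non-randomised comparison, and the protocol itself describes the spread of a technique that it cites as reducing ventilation. If dosing drifts as well, part of the drift would be attributed to dose, and neither specified analysis would reveal it.

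Under the assumed shifts the spurious difference is about 1.5 to 4.5 points, one tenth to three tenths of the 15-point design effect. The false-positive rate is about 7% to 27% against a nominal 5%. This rests on two equal halves, no true dose effect and no absorption of drift by the seven factors. None of these cases comes near to producing the full design effect by itself. The omission is a gap in protection that is cheap to close and does not by itself invalidate the study.

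**What to change.** Add quarter or half-year of birth, a coarse item, to the requested fields in section 3a and Appendix A, and state that it is kept in the study file. In section 6, include it as a categorical term in the propensity model and in the outcome model, for both the matched analysis and the unmatched key sensitivity analysis.

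The cost is one coarse data item, a few degrees of freedom and, if practice changes sharply, possibly slightly fewer matches. It should be settled before the data request is final.

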## NNRD Fields

Surfactant can be administered prophylactically (usually within the delivery room) or as rescue (usually within the neonatal ward). If surfactant is given prophylactically, it is assumed that this is the first administration.

If administered prophylactically, it is proposed that the following data items are added under the 'NNUEpisodes-Labour & Delivery' category within the electronic record:

	Question	Answer
1	Volume of surfactant administered in millilitres (mL)	[free text box]
2	Method of surfactant administration	
 
• Endotracheal tube
 
• INSURE (endotracheal tube in place for 15 minutes or less)
 
• Thin catheter for minimally invasive/less invasive surfactant administration
 
• Other
 

3	Time of initial surfactant administration	[free text]
4	Specify any analgesics and/or sedatives used for surfactant administration (drug and dose)	[free text]

Surfactant can also be administered in a rescue setting, usually within the neonatal unit. In this setting, the frequency of administration is captured (i.e. whether this is the infant's first, second or third dose). The following fields are proposed under the 'Respiratory-Daily' category:

	Question	Answer
1	Volume of surfactant administered in first dose, millilitres (mL)	[free text box]
2	Specify the method of surfactant administration	
 
• Endotracheal tube
 
• INSURE (endotracheal tube in place for 15 minutes or less)
 
• Thin catheter for minimally invasive/less invasive surfactant administration
 
• Other
 

3	How many doses of surfactant were administered today?	[Free text box]
4	Time of initial surfactant administration	[free text]
5	Specify any analgesics and/or sedatives used for surfactant administration (drug and dose)	[free text]
6	FiO 2 at point of decision to administer surfactant	
 
• < 30 %
 
• 30- 39 %
 
• 40 - 49 %
 
• 50 - 59 %
 
• ≥ 60 %
 

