**The effect of surfactant dose on outcomes in preterm infants with RDS**

19	Medication > Drugs given on this day	To identify infants who have received surfactant during their hospitalisation period, and which surfactant To identify which infants received analgesics or sedatives on the same day as surfactant, and which babies were given postnatal steroids
20	Two year follow up > Respiratory & CVS system – On supplemental oxygen or any respiratory support?	To determine whether the dose of surfactant is related to whether the infants requires supplemental oxygen at 2 years
21	Two year follow up > Development – at 24 month corrected age***	To determine whether the dose of surfactant is related to infant development (normal or mild, moderate or severe delay).
22	Two year follow up > Bayley III cognitive, total raw score	To determine whether the dose of surfactant is related to the infant's cognitive ability

\*There are two NNRD fields for this outcome (right and left eye)

\*\*There are two NNRD fields for this outcome (right and left side)

\*\*\*There are four NNRD fields for this outcome (normal and mild, moderate or severe delay)

The full list of NNRD fields can be found in Appendix A.

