## 12. Appendix A

Category	Category Detail	Item Name	Field ID	NHS data Dictionary Item Name	Format/Length	Coding/allowed values	Description	Purpose
NNUEpisodes	Demographics and Birth Information (Baby)	Birth weight (g)	Birthweight	BIRTHWEIGHT	N4	Accepted range is between 001-9998g...9999 Unknown	Birth weight at the time of delivery in grams	Used to identify risk factors on admission to neonatal care
NNUEpisodes	Demographics and Birth Information (Baby)	Sex of the baby (phenotypic)	SexPhenotype	PERSON PHENOTYPIC SEX	N1	1 Male 2 Female 9 Indeterminate/Intersex	The sex of the baby. 'Not known' is an option if information is missing or not recorded. 'Not specified' is an option for instances where the sex cannot be determined at birth.	Used to aggregate data by sex
NNUEpisodes	Demographics and Birth Information (Baby)	Gestation age in weeks	GestationsWeeks	GESTATION LENGTH (AT DELIVERY)	N2	10-49	The best obstetric estimate at the time of delivery in weeks. This will normally be based on the postmenstrual age but, if appropriate, may be modified on the basis of antenatal ultrasound. Where gestation at delivery is not known, this is based on the postnatal estimate of maturity	Used to identify risk factors on admission to neonatal care

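### The primary analysis set requires baseline FiO2, which is collected only for rescue surfactant, so infants whose first dose was prophylactic all drop out

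*Protocol*

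**What the plan says.** - **Model and analysis set (Section 6).** The primary comparison of 100-130 with 170-200 mg/kg uses 1:1 propensity score matching. The model's seven factors include "antenatal steroids, inborn, age at first dose, and baseline" FiO2. The mITT population is limited to infants "who provide complete data on each of the baseline factors considered for inclusion in the propensity model" who are also evaluable for the primary endpoint. The key sensitivity analysis compares the unmatched dosing groups in the full mITT population.
- **Prophylactic form (Section 3, NNRD Fields).** "If administered prophylactically, it is proposed that the following data items are added": volume, method, time, and analgesics or sedatives. FiO2 is not among them. The same section assumes that a prophylactic dose is the infant's first.
- **Rescue form (same section).** Six items. The sixth is FiO2 "at point of decision to administer surfactant", in five bands.
- **Eligibility (Sections 1 and 4b).** Surfactant treatment is required, with no distinction between prophylaxis and rescue.
- **Extracted fields (Section 3a).** After the table of database fields it states: "The full list of NNRD fields can be found in Appendix A". Neither list contains an FiO2 field, inborn status, or a date or time of birth.

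**The concern.** Section 6 demands a covariate that Section 3 arranges to collect in only one of the two settings it describes. The complete-case rule then removes a whole treatment setting, not a scatter of incomplete records.

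That setting matters to the question. Section 2b gives dosing shortly after birth, before the weight is known, as a reason for whole-vial use, and whole-vial use is the practice that motivates the study. Section 7 also foresees prophylactic use. If these infants drop out, the primary estimate applies to a narrower population than the eligibility criteria describe.

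The planned checks would not reveal it. The key sensitivity analysis has the same exclusion, and the interim look at the first 400 infants in Section 4a checks only the split between dosing groups.

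**Working it through.** **1. Follow one infant through the rules.** Take an eligible infant whose first dose is prophylactic.

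| Step | Source | Result |
|---|---|---|
| Eligible? | Section 4b | Yes |
| Is this dose the studied exposure? | Section 3 (prophylactic dose taken as first); primary objective (first dose) | Yes |
| Is FiO2 recorded for this dose? | Section 3, prophylactic form | No such item |
| Is FiO2 listed elsewhere? | Section 3a and Appendix A | No |
| Complete on all propensity factors? | Section 6 | No |
| In the matched primary analysis? | Section 6 | No |
| In the key sensitivity analysis? | Section 6, same mITT | No |

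**2. Could a later rescue record supply the value?** A prophylactic infant who is dosed again on the unit would have an FiO2 on the rescue form. That value follows the first dose and may be affected by it, so it is not baseline. Only re-dosed infants would have one, and re-dosing is itself an outcome in the secondary objectives. Using it would admit prophylactic infants selectively according to an outcome.

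**3. How many infants?** The prophylactic share f is not in the protocol, so f is an assumption. Infants left = 1300 × (1 − f): 1170 at 10%, 1040 at 20%, 910 at 30%, 780 at 40%, 650 at 50%.

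**4. Does this show a loss of power?** First reproduce the plan's table for 60% against 45%, 80% power, two-sided 5%:

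- n per group = (1.960 + 0.842)² × (0.60×0.40 + 0.45×0.55) / 0.15² = 171 after rounding up.
- Table total = 2n / (smaller-group share × 0.75): 342/0.3375 = 1014; 342/0.30 = 1140; 342/0.2625 = 1303. All three match the plan.

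Now take f = 30% at the 35%/55% split, assuming the split is the same among rescue infants. Power = Φ(0.15/√(0.4875/n) − 1.960).

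- Section 4a's text says the smaller group determines the matched sample. Pairs = 910 × 0.35 × 0.75 = 239, against 1300 × 0.35 × 0.75 = 341 with no loss. With n = 239 per group, power is about 91%. At f = 50%, 171 pairs remain, with 80.1% power.
- The table instead divides 2n by the smaller group's share. On that accounting n is half the number of pairs, 119.4 per group at f = 30%, and power is 65.1%, against 80.1% with no loss.

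The two accountings disagree, and the one that follows 1:1 matching leaves enough pairs. A shortfall is therefore not established.

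**The case against.** **The SAP may settle it.** The protocol does not define baseline FiO2, and a SAP could. But a SAP cannot supply a value that was never recorded, and the covariate list and complete-case rule are fixed in the protocol. The database holds about 450 items and might contain another usable FiO2 field. If so, none is listed for this study.

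**A rescue-only comparison may be close to the real question.** The title, objective and rationale speak of infants with RDS, whereas eligibility asks only for surfactant treatment. This has some force: restricting the primary comparison to rescue infants could be defended. It should then be a stated choice, not a by-product of a form.

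**Stronger readings that the protocol does not support:**

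- *The model cannot be fitted, or no infant is complete.* A reader might infer this because inborn status and birth time are unlisted. But the lists are visibly not the whole dataset: Appendix A also omits the new study items, and the Section 3a numbering jumps from 14 to 16. Endpoints counted from birth, and a field meant to give age at discharge, imply that a birth reference will be supplied. Inborn status is an omission from a list, correctable when the extract is ordered.
- *FiO2 is never collected for delivery-room surfactant.* The forms follow prophylaxis and rescue, which Section 3 ties to place only as the usual case.
- *Gestation is inadequately captured.* Appendix A has "Gestation age in weeks" while Section 3a lists weeks and day. This is clerical; completed weeks suffice for the eligibility boundary.
- *The study becomes underpowered.* Not shown, as the working explains.

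**Conclusion.** The contradiction between Sections 3 and 6 stands and affects the primary analysis. On the listed fields, every infant whose first dose was prophylactic is excluded by rule from both the matched analysis and the key sensitivity analysis, although eligible. The exclusion of that group is complete whatever its size; the size itself cannot be derived from the protocol.

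This rests on two readings: that baseline FiO2 means FiO2 before the first dose, and that no unlisted FiO2 field will be used. The consequence is an unstated restriction of the primary result to rescue-treated infants. The missing listings for inborn status and age at first dose are a secondary point to check.

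**What to change.** 1. Add the banded FiO2 item to the prophylactic form.
2. Where surfactant was given without an FiO2-based decision, code prophylactic as its own level of the FiO2 factor, and amend the mITT definition so that this level counts as complete.
3. If neither is done, state in the objective and in Section 6 that the primary comparison applies to rescue-treated infants only.
4. As a secondary check, add inborn status and a derived, anonymised age at first dose to Section 3a and Appendix A. A derived age avoids extracting a raw time of birth.

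The cost is one form item, one factor level, two entries in the field lists and an edit to the mITT definition. Infants coded to the prophylactic level would not be adjusted for FiO2 within that level, which the report should acknowledge. The form item has to be in place before data are collected; a value that was not recorded cannot be restored by the analysis.

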## 4. Study Population

### a. Number of Participants

*Proposed sample size: 1300*

The study is powered based on assumed proportions requiring mechanical ventilation within 72 hours of 60% and 45% in the dosing groups 100-130 mg/kg and 170-200 mg/kg respectively. The required power is 80% with the treatment comparison being undertaken at the two-sided 5% level of significance. At the planning stage the proportions of patients falling into the two dosing groups is not known. The sample size for the propensity score matched analysis is determined by the smaller of the two dosing groups and also the ability to find a match for each infant in that group. The table below provides total sample sizes required based on the assumptions set down according to various splits for the proportions of infants in the two dosing groups. Note also that the assumption has also been made that 10% of infants will receive a dose that falls between the upper limit of the lower dose group and the lower limit of the higher dose group. We will also assume that for 25% of infants in the smaller dosing group a match cannot be found. Sample sizes for 90% power are provided for completeness.

The proposed initial sample size of 1300 covers a range of possible assumptions regarding the split across the dosing groups including 45%/45%, 40%/50% and 35%/55%. An interim evaluation of the proportions of infants who fall into the two dosing groups will be undertaken on the first 400 infants recruited into the study to provide a check of the assumed breakdown and a sample size change considered if these assumptions are not correct.

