## 5. Data and Research Management

Selected study sites for participation will be approached to allow healthcare professional the opportunity to discuss the study and its aims. Data champions will be appointed at each study site; their responsibility will be to ensure data are fully recorded on all eligible infants who have provided opt-out consent.

Confirmation of quality assurance will be obtained from the NNRD every 3 months. No patient identifiers, or individual Trust identifiers, will be included in this study file.

Interim anonymised data will be analysed by an independent statistician within 3 months of the last patient recruited reaching 28 days post birth. All data will be anonymised and shall include no individual patient data.

The final anonymised data will be analysed by an independent statistician within 3 months of completion of the study (when the last patient has reached the 2 year time point). All data will be anonymised and shall include no individual patient data.

Once the final analysis of the data has been carried out, the original data will be destroyed. The analysed data will be kept by Chiesi for a minimum period of 5 years to allow dissemination.

This is an observational study, and the NNRD hold the relevant permissions for the data to be provided in anonymised form for the purposes of research by parties other than the NNRD upon specific Research Ethics Committee approval. Opt-out consent will be gained from the parents of babies eligible for inclusion in the study to confirm that they are happy for their baby's data to be utilised for this study.

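### Multiples are eligible, but the listed fields cannot identify siblings, so the analysis as specified cannot allow for sibling clustering; the likely effect on standard errors and the 5% level is modest and can go either way

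*Protocol*

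**What the plan says.** **Eligibility.** Protocol sections 1 and 4b admit surfactant-treated infants of 36+6 weeks or less with a recorded birth weight, birth after study start and opt-out consent. The only exclusion is gestation of 37+0 weeks or more. Nothing limits entry to one infant per pregnancy.

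**Data requested.** Section 3 lists the new surfactant items and section 3a the existing database items. Section 3a adds: "The full list of NNRD fields can be found in Appendix A". None of these lists contains number of fetuses, birth order, a maternal item or a birth-set number.

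**De-identification.** Section 5 states: "No patient identifiers, or individual Trust identifiers, will be included in this study file". No date of birth is listed either.

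**Analysis.** For the primary comparison section 6 says that "an analysis of the matched cohorts will be based on a logistic regression model with the primary endpoint" as response. The terms are dosing group and the seven propensity covariates: birth weight, gestational age, sex, antenatal steroids, inborn, age at first dose and baseline FiO2. The key sensitivity analysis uses the same model on the unmatched groups. Neither description mentions siblings, a cluster term or a robust variance.

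**Level and power.** Section 4a: "The required power is 80% with the treatment comparison being undertaken at the two-sided 5% level of significance".

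**The concern.** Siblings from one pregnancy share gestation, antenatal steroid exposure, place of birth and often the treating team, so their outcomes are likely to be correlated. Their doses may be too. Dose is calculated from volume and birth weight (section 3a), and section 2b says whole-vial dosing is the more frequent practice. Co-twins of similar weight given the same vial would land close together in mg/kg; co-twins of different weight could land in different bands.

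A model that treats such infants as independent gives standard errors that are too small when siblings sit in the same dose group and too large when they sit in opposite groups.

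Choosing a variance estimator is ordinary analysis-plan material. The list of fields is not: this protocol fixes it. Without a birth-set key the analyst can neither cluster on siblings nor run a sensitivity analysis to see whether clustering mattered. Without a multiplicity item, multiple birth cannot even be described by dose group.

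**Working it through.** **1. The protocol's own figure.** Inputs from section 4a: event rates 60% and 45%, two-sided 5%, 80% power, 25% of the smaller group unmatched, and 10% of infants between the bands.
- n per group = (1.96 + 0.8416)² × (0.60×0.40 + 0.45×0.55) / 0.15² = 170.06, rounded up to 171.
- Tabled total = 2 × 171 / (0.75 × share of the smaller group). This gives 1014 at 45/45, 1140 at 40/50 and 1303 at 35/55.

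All three match the table. The formula leaves no room for a clustering allowance.

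**2. Effect of ignoring twins.** Let f be the share of analysed infants whose co-twin is also analysed, ρ the residual within-set correlation of the outcome, and c the share of pairs in the same dose group.
- Variance ratio: D = 1 + (2c − 1) × f × ρ.
- True level of the unadjusted test: 2 × [1 − Φ(1.96/√D)].

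The documents give none of f, ρ or c, so all three are assumptions.

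| f | ρ | D, all pairs same group | Reported SE ÷ true SE | True level | D, all pairs split | True level |
|---|---|---|---|---|---|---|
| 0.20 | 0.2 | 1.040 | 0.981 | 5.5% | 0.960 | 4.6% |
| 0.25 | 0.3 | 1.075 | 0.964 | 5.9% | 0.925 | 4.2% |
| 0.35 | 0.5 | 1.175 | 0.923 | 7.1% | 0.825 | 3.1% |

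With half the pairs concordant (c = 0.5), D = 1 and the level is 5%. With c = 0.8, the first and last rows give 5.3% and 6.2%.

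**3. Matching losses.** The table takes f from the whole cohort, but matching discards infants. On section 4a's assumptions, 75% of the smaller group is kept.
- At 35/55, 0.35 × 0.75 / 0.55 = 0.477 of the larger group is kept. If co-twins are retained independently, the effective share is f × (0.75 + 0.477)/2 = 0.61f.
- At 45/45 it is 0.75f.

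With every pair still in one group, the level runs from 5.3% (f = 0.20, ρ = 0.2, factor 0.61) to 6.5% (f = 0.35, ρ = 0.5, factor 0.75). If co-twins tend to be retained together, the reduction is smaller.

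**4. Null simulation.** 1300 infants, 35/10/55 split, 75% of the smaller group kept, an equal number drawn at random from the larger group as a stand-in for matching, unadjusted two-proportion test, 8000 runs per setting (Monte Carlo SE about 0.24 points). Between 20 and 30% of infants were twins, and the latent outcome correlation was 0.3 to 0.8, roughly 0.19 to 0.59 on the binary scale by (2/π) × arcsin.
- Co-twins' doses unrelated: rejection 4.5 to 5.4%.
- Latent dose correlation 0.5 or 0.9: rejection 5.1 to 6.1%.

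**5. Power.** At N = 1300 and 35/55, 1300 × 0.35 × 0.75 gives 341 matched pairs and power 97.6%. Dividing 341 by D = 1.175 gives 95.3%. The margin exists because the tabled formula places the two-group total, 342, in the smaller group, where 171 pairs already give 79.6%.

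**The case against.** **The variance method belongs to the analysis plan.** Section 6 never says that infants are assumed independent, and a logistic regression with clustered standard errors is still a logistic regression. Section 10 refers to a pre-agreed analysis plan that is not shown. This stands: silence on the estimator is not in itself a fault. It does not supply the missing field.

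**A reader might infer that the error bars and the 5% level are simply wrong.** The documents do not support that. The share of multiples, the residual correlation and the dose concordance of co-twins are all unstated, and the error can be conservative. Gestation and antenatal steroids are already in the outcome model, so only correlation left after adjustment counts.

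**A reader might infer that the problem cannot be repaired later.** That is not supported either. Section 9a gives an amendment route, section 3 describes a source of about 450 items, and section 5 destroys the original data only after the final analysis. A random set number is neither a patient nor a Trust identifier, so section 5 does not bar it. The appendix is also not a firm boundary: inborn status is a model covariate but appears in no field list, so at least one field must be added anyway. What remains is narrower: no repair is possible from the extract as listed, and the key must be requested while the original data exist.

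**A reader might extend this to every secondary and exploratory analysis.** Section 6 names no models for those, so no size can be put on it.

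**Conclusion.** The point holds in limited form. Multiples are eligible, and the field list described as full offers no means of grouping siblings reliably. The analysis as specified therefore cannot account for them. That gap does not depend on any assumed correlation.

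Its numerical consequence does. The range of about 5.5 to 7.1% is an upper bound for the stated inputs: 20 to 35% of infants in twin sets, residual correlation 0.2 to 0.5, every pair in one dose group and no matching loss. Matching losses alone bring it to about 5.3 to 6.5%; discordant pairs lower it further and can take it below 5%. The simulation stayed between 4.5 and 6.1%. The distortion is probably modest, its direction is not fixed by the documents, and power at 1300 is not threatened under section 4a's assumptions. It is worth correcting because the correction is cheap and has to be made before the data are drawn and destroyed.

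**What to change.** Before extraction, add two items to section 3a and Appendix A:
- a random, non-identifying birth-set number;
- a multiple-birth indicator.

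Whether the source database can supply them must be confirmed with its holders; the protocol does not show it.

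In section 6, state that the matched and unmatched logistic regressions use standard errors clustered on birth set. Describe multiple birth by dose group. Adding it to the propensity model is optional, since nothing in the documents shows that it confounds dose group beyond birth weight and gestation.

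The cost is one or two more data items, a sentence of analysis wording and, if co-twins mostly share a dose group, slightly wider intervals.
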